6.1 Exposure to Study Treatment(s)

The study drug administration will be summarized by treatment group with descriptive statistics, including cystoscope type (Flexible, Rigid), number of injection site, total volume injected. The summary will be done for double-blind and open-label period separately.

Details pertaining to the administration of study drug will be listed, including use of anesthesia, cystoscope type, date/time of injection, number of injection site, total volume injected, location of injections, etc.

Prophylactic antibiotics are to be administered beginning 1 to 3 days before study treatment, on the day of study treatment, and continuing for 1 to 3 days after study treatment. The investigator is to prescribe the appropriate antibiotic and number of days pretreatment and post treatment based on clinical judgment and local site practice. Details of prophylactic antibiotics will be listed. Treatment period for prophylactic antibiotics will be derived using the similar logic as for concomitant medication. Please refer to [Table 6](#) for the detailed classification.

6.2 Concomitant Medications

Concomitant medications are medications which started before initiation of DB treatment and continued into DB treatment or started after the initiation of the DB treatment. For re-treated subjects, the concomitant medications started before the initiation of OL treatment will be assigned to double-blind period. The concomitant medications started before the initiation of OL treatment and continued into OL treatment or started on or after the initiation of the OL treatment will be assigned to open-label period. Please refer to [Table 6](#) for the detailed classification.

Concomitant medications are coded with WHODDE, and will be summarized by chemical subgroup (ATC 4th level) and preferred WHO name by treatment group for the Safety Population. Summary for concomitant medications will be based on safety population for those concomitant medications assigned to double-blind period and subjects who entered open-label re-treatment period for those concomitant medications assigned to open-label period.

Subjects taking the same medication multiple times will be counted once per medication. A medication that can be classified into several chemical subgroups is presented in all chemical therapeutic subgroups.

Table 6: Classification of Concomitant Medications (CMs) by Treatment Period

Subjects not re-treated:

Medication Start Date	Medication Stop Date	Medication Classification
CM start date < DB Treatment start date	CM stop date >= DB Treatment start date OR ongoing	DB period
CM start date >= DB Treatment start date		DB period

Subjects re-treated:

Medication Start Date	Medication Stop Date	Medication Classification
CM start date < OL Treatment start date	CM stop date >= OL Treatment start date OR ongoing	OL period
CM start date >= OL Treatment start date		OL period
CM start date < OL Treatment start date	CM stop date >= DB Treatment start date and CM stop date < OL Treatment start date	DB period
CM start date < OL Treatment start date	CM stop date >= OL Treatment start date	DB period, OL Period
CM start date < OL Treatment start date	Ongoing	DB period, OL Period
CM start date >= DB Treatment start date	CM stop date < OL Treatment start date	DB period
CM start date >= DB Treatment start date	CM stop date >= OL Treatment start date	DB period, OL Period
CM start date >= DB Treatment start date	Ongoing	DB period, OL Period

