**Treatment 2:**

A second treatment may be administered provided the patient qualifies for Treatment 2 (see below criteria) and only if the Day of Treatment Criteria are fulfilled. All patients will receive BOTOX 100 U for their second treatment. The Qualification for Treatment 2 can occur any time starting at Week 12 up to Week 30 post Treatment 1 and must occur during a clinic visit, either at a regular prescheduled visit or an additional unscheduled visit, depending on the timing of the request for a second treatment. If the patient does not request a second treatment, then the Week 30 clinic visit will be an exit visit.

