## **8.7 Compliance with Protocol**

Participating patients must be able to adhere to the diary completion and testing parameters as described in this protocol.

Data will be recorded on the appropriate eCRF supported by appropriate source documentation. At each clinic visit and at the phone contact at Week 1, patients should be asked if any concomitant medications have been used or if they have undergone any concurrent procedures (non-study procedures), as well as their compliance with the protocol since the previous clinic visit/phone conversation. If medications were taken for UTI, the UTI medication name should be recorded separately from other concomitant medications, in the designated field in the CRF.

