6.3 Concomitant Procedures

Concomitant procedures (including catheterization with associated frequency and reason for catheterization) will be listed. Concomitant procedures will be coded in Medical Dictionary for Regulatory Activities (MedDRA, Version 19.0 or later).

Treatment period for concomitant procedure will be derived using the similar logic as for concomitant medication. Please refer to [Table 6](#) for the detailed classification. Concomitant procedures will be summarized.

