6.5 Adverse Events

Treatment-Emergent Adverse Events (TEAEs) are defined as those that begin on or after initiation of first dose of study treatment. For re-treated subjects, the TEAEs started on or after the initiation of DB treatment and before the initiation of OL treatment will be assigned to double-blind period. The TEAEs started on or after the initiation of OL treatment will be assigned to open-label period. Refer to [Table 7](#) for the classification of TEAEs by treatment period as:

- Double-blind period
- Open-label period

Table 7: Classification of TEAEs

Subjects not re-treated:

TEAE Start Date/Time	TEAE Classification
DB Treatment start date/time <= AE start date/time	Double-Blind period

Subjects re-treated:

TEAE Start Date/Time	TEAE Classification
DB Treatment start date/time <= AE start date/time < OL Treatment start date/time	Double-Blind period
AE start date/time >= OL Treatment start date/time	Open-Label period

Adverse events will be classified by type, incidence, severity, and causality. The overall incidence of AEs will be summarized using the MedDRA coding system and classified by SOC, PT, and treatment group.

An overall summary table will present the number of events and the incidence of subjects having at least one event in the following categories:

- TEAEs
- TEAEs indicated as serious (SAEs)
- TEAEs leading to study discontinuation
- TEAEs leading to death
- TEAEs related to study drug
- Serious TEAEs related to study drug
- Possible distant spread of toxin (PDSOT) TEAEs (refer to [Section 6.5.2](#))
- TEAEs of urinary retention (Refer to [Section 6.5.1](#))
- TEAEs of residual urine volume (Refer to [Section 6.5.1](#))
- TEAEs of urinary tract infection (Refer to [Section 6.5.1](#))
 - TEAEs of asymptomatic urinary tract infection
 - TEAEs of symptomatic urinary tract infection

Tabulation (using counts and percentages) of TEAEs classified by SOC and PT will be provided. In addition, Tabulation of TEAEs classified by SOC and PT will be provided for each of the following:

- Serious TEAEs
- Treatment-Related Serious TEAEs
- TEAEs leading to study discontinuation
- Treatment-related TEAEs leading to study discontinuation

Tabulation of TEAEs classified by PT will be provided for each of the following:

- TEAEs
- Serious TEAEs
- TEAEs by maximum severity
 - Subjects with multiple TEAEs with the same PT will be summarized at the maximum severity and counted one time for that PT.
- TEAEs related to study drug

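### SAP Table 6 contradicts itself for re-treated subjects: two rows also place items begun after open-label BOTOX in the double-blind period

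*SAP*

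**What the plan says.** SAP 6.2 gives the rule for re-treated subjects in words. For items begun before open-label (OL) treatment, "the concomitant medications started before the initiation of OL treatment will be assigned to double-blind period". If such an item continues into OL treatment, the text also places it in the open-label period. Items that "started on or after the initiation of the OL treatment will be assigned to open-label period" belong to that period only. The text then refers the reader to Table 6 for the detailed classification, and the period label decides which summary an item enters.

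The rows of Table 6 are not numbered. Counted from the top of the re-treated part, they say:

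| Row | Start date | Stop date | Label |
|---|---|---|---|
| 1 | before OL | on or after OL start, or ongoing | OL |
| 2 | on or after OL start | any | OL |
| 3 | before OL | on or after double-blind (DB) start, before OL | DB |
| 4 | before OL | on or after OL start | DB and OL |
| 5 | before OL | ongoing | DB and OL |
| 6 | on or after DB start | before OL | DB |
| 7 | on or after DB start | on or after OL start | DB and OL |
| 8 | on or after DB start | ongoing | DB and OL |

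The start condition in rows 6 to 8 is "CM start date >= DB Treatment start date", with no upper limit. Table 6 states no order of precedence among rows.

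The same logic is used elsewhere. SAP 6.3 says: "Treatment period for concomitant procedure will be derived using the similar logic as for concomitant medication". Procedures, which include catheterization, are both listed and summarized. SAP 6.1 says: "Treatment period for prophylactic antibiotics will be derived using the similar logic as for concomitant medication". Those antibiotics are listed.

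**The concern.** An item begun on or after OL treatment satisfies row 2 (OL only). It also satisfies row 7 if it has stopped or row 8 if it is ongoing, and both of those rows add the DB label. The table and the text therefore disagree about the same dates, and the text sends the programmer to the table.

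What is at stake is which treatment an item is attributed to. Under the protocol's description of Treatment 2, "All patients will receive BOTOX 100 U for their second treatment". For a re-treated placebo patient, everything begun after that injection is experience on BOTOX. If rows 7 and 8 are programmed as printed, such an item could also be counted in the placebo column of the double-blind summary. The items include some of interest here: Protocol 8.7 asks that "If medications were taken for UTI, the UTI medication name should be recorded separately from other concomitant medications", and the procedures in SAP 6.3 include catheterization.

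**Working it through.** **Inputs.** The eight re-treated rows of Table 6 and the wording of SAP 6.2. The plan states no figure on this point to reproduce, so the check is one of logic.

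**Patterns.** Start can be before DB, in the DB period, or in the OL period. Stop can be in the DB period, in the OL period, or ongoing. That gives 3 × 3 = 9 patterns. One is impossible (start in OL, stop in DB), which leaves 8. An item that ended before DB treatment is a prior medication under SAP 4.3 and is left out.

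| Start | Stop | Rows met (label) | SAP 6.2 text |
|---|---|---|---|
| before DB | in DB | 3 (DB) | DB |
| before DB | in OL | 1 (OL), 4 (both) | both |
| before DB | ongoing | 1 (OL), 5 (both) | both |
| in DB | in DB | 3 (DB), 6 (DB) | DB |
| in DB | in OL | 1 (OL), 4 (both), 7 (both) | both |
| in DB | ongoing | 1 (OL), 5 (both), 8 (both) | both |
| in OL | in OL | 2 (OL), 7 (both) | OL |
| in OL | ongoing | 2 (OL), 8 (both) | OL |

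**Conflicts.** If each item should receive one row's label, 6 of 8 patterns meet rows with different labels.

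**Possible ways to resolve them.**
- Additive (an item takes every period named by any row it meets). The four conflicts from row 1 disappear, because OL added to DB and OL is still both, as the text requires. The last two patterns come out as both, where the text says OL only. Result: 2 of 8 wrong.
- First matching row from the top. Row 2 now correctly settles the last two patterns, but row 1 gives OL only for the four patterns that begin before OL and continue into it. Result: 4 of 8 wrong.
- Last matching row. Rows 7 and 8 decide the last two patterns. Result: 2 of 8 wrong.

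None of these readings reproduces the text.

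**After correction.** With rows 7 and 8 limited to starts before OL and row 1 deleted, no pattern has conflicting labels and none departs from the text (0 of 8). Rows 2 to 5 alone do the same: row 3 covers both patterns that stop in DB, rows 4 and 5 cover the four that continue into OL, and row 2 covers the two that start in OL.

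**Size.** The protocol randomizes at least 114 at 2:1, so about 114/3 = 38 receive placebo. One patient is 1/38 = 2.6 percentage points of a placebo double-blind percentage. It is up to 2.6 because a patient already counted on that line for a genuine double-blind item adds nothing; SAP 6.2 counts a subject once per medication.

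**The case against.** The best reply is that the intention is plain. Row 2 and the text both say open-label only, and a careful programmer would follow them. That stands in part: this is a self-contradiction, not a table that is wrong throughout, and the final tables may come out right. But the SAP names Table 6 as the detailed rule and gives no precedence, and taking rows in printed order repairs rows 7 and 8 only by letting row 1 misclassify the items that span the second injection.

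A reader might also take row 1 against rows 4 and 5 as a second error. The documents do not support that. The text puts an item begun before OL treatment in the double-blind period and, if it continues, in the open-label period too. Row 1 can be read as supplying the second half of that rule, so it is redundant.

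A further reply is that the reach is small, and this stands. SAP 6 plans no inferential comparison for safety, so no test or error rate is touched. Prophylactic antibiotics for Treatment 2 begin 1 to 3 days before the injection (Protocol 5.9.2), so they do not fall under the faulty rows, and they are only listed.

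**Conclusion.** The point holds as a minor error of specification. Rows 7 and 8 of the re-treated part of Table 6 contradict row 2 and the SAP 6.2 text for every item begun on or after open-label BOTOX. If they are programmed as printed, medication summaries (SAP 6.2) and procedure summaries (SAP 6.3) could carry post-BOTOX items in the placebo double-blind column, at up to 2.6 points per affected patient. This assumes about 38 placebo patients in the summary. The number affected cannot be derived from the documents, so no total effect is claimed.

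Two stronger readings are not supported. A reader might infer that adverse event counts are contaminated in the same way. They are not: SAP 6.5 says "the TEAEs started on or after the initiation of DB treatment and before the initiation of OL treatment will be assigned to double-blind period", later events go to the open-label period, and the two parts of Table 7 for re-treated subjects do not overlap. A reader might also infer, because Table 7 sets no Week 12 limit, that the plan lacks an equal-window comparison of adverse events. SAP 7 already plans safety results for the first 12 weeks as a subset of the final analyses, and SAP 3.2 summarizes the duration of the double-blind period. SAP 2.2, SAP 6.4 and the table mocks, where a cut could be defined, are not visible.

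Rules for summarizing clean intermittent catheterization that lie outside the visible text could not be checked, so nothing is claimed about those summaries.

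**What to change.** In the re-treated part of Table 6, keep only rows 2 to 5. They are mutually exclusive and reproduce the SAP 6.2 text for all eight patterns. Alternatively, add to rows 7 and 8 the condition that the start date falls before the OL treatment start date, and delete row 1. This is also correct, but it leaves rows 6 to 8 as duplicates of cases already covered by rows 3 to 5.

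Sections 6.1 and 6.3 refer to Table 6, so they need no edit of their own. The cost is a few table rows in a SAP revision and a check that the period-assignment code follows them. No new data and no additional outputs are needed.

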6.3 Concomitant Procedures

Concomitant procedures (including catheterization with associated frequency and reason for catheterization) will be listed. Concomitant procedures will be coded in Medical Dictionary for Regulatory Activities (MedDRA, Version 19.0 or later).

Treatment period for concomitant procedure will be derived using the similar logic as for concomitant medication. Please refer to [Table 6](#) for the detailed classification. Concomitant procedures will be summarized.

6.5 Adverse Events

Treatment-Emergent Adverse Events (TEAEs) are defined as those that begin on or after initiation of first dose of study treatment. For re-treated subjects, the TEAEs started on or after the initiation of DB treatment and before the initiation of OL treatment will be assigned to double-blind period. The TEAEs started on or after the initiation of OL treatment will be assigned to open-label period. Refer to [Table 7](#) for the classification of TEAEs by treatment period as:

- Double-blind period
- Open-label period

Table 7: Classification of TEAEs

Subjects not re-treated:

TEAE Start Date/Time	TEAE Classification
DB Treatment start date/time <= AE start date/time	Double-Blind period

Subjects re-treated:

TEAE Start Date/Time	TEAE Classification
DB Treatment start date/time <= AE start date/time < OL Treatment start date/time	Double-Blind period
AE start date/time >= OL Treatment start date/time	Open-Label period

Adverse events will be classified by type, incidence, severity, and causality. The overall incidence of AEs will be summarized using the MedDRA coding system and classified by SOC, PT, and treatment group.

An overall summary table will present the number of events and the incidence of subjects having at least one event in the following categories:

- TEAEs
- TEAEs indicated as serious (SAEs)
- TEAEs leading to study discontinuation
- TEAEs leading to death
- TEAEs related to study drug
- Serious TEAEs related to study drug
- Possible distant spread of toxin (PDSOT) TEAEs (refer to [Section 6.5.2](#))
- TEAEs of urinary retention (Refer to [Section 6.5.1](#))
- TEAEs of residual urine volume (Refer to [Section 6.5.1](#))
- TEAEs of urinary tract infection (Refer to [Section 6.5.1](#))
 - TEAEs of asymptomatic urinary tract infection
 - TEAEs of symptomatic urinary tract infection

Tabulation (using counts and percentages) of TEAEs classified by SOC and PT will be provided. In addition, Tabulation of TEAEs classified by SOC and PT will be provided for each of the following:

- Serious TEAEs
- Treatment-Related Serious TEAEs
- TEAEs leading to study discontinuation
- Treatment-related TEAEs leading to study discontinuation

Tabulation of TEAEs classified by PT will be provided for each of the following:

- TEAEs
- Serious TEAEs
- TEAEs by maximum severity
 - Subjects with multiple TEAEs with the same PT will be summarized at the maximum severity and counted one time for that PT.
- TEAEs related to study drug
- TEAEs leading to death

When reporting the number of TEAEs, if the same TEAE occurs for a subject on multiple occasions the event will be counted once for each occurrence.

All adverse events and related details will be listed by treatment group and subject. Non-treatment-emergent events will be identified in all listings, but not included in summaries.

6.5.1 Study-specific Definitions for Particular Adverse Events

All particular AEs (AE of urinary retention, AE of residual urine volume, and AE associated with possible distant spread of toxin (PDSOT)) and treatment-related particular AEs will be tabulated by SOC and PT; in addition, all particular AEs will be listed by treatment group and subject.

6.5.1.1 Definition of Adverse Event of Urinary Retention:

An adverse event of urinary retention should only be recorded when a subject has a raised PVR urine volume that requires intervention with CIC according to the following criteria:

- Subject has a PVR urine volume of ≥ 350 mL (regardless of symptoms), OR
- Subject has a PVR urine volume ≥ 200 mL and < 350 mL and the subject reports associated symptoms i.e., voiding difficulties, sensation of bladder fullness that in the investigator's opinion require CIC.

6.5.1.2 Definition of Adverse Event of Residual Urine Volume:

An adverse event of residual urine volume should be recorded if, in the investigator's opinion, the raised PVR urine volume is clinically significant but does not fulfill the above definition for urinary retention.

6.5.1.3 Definition of Adverse Event of Urinary Tract Infection:

An adverse event of UTI will be recorded if both the following criteria are fulfilled, regardless of subject symptoms:

- A positive urine culture result with a bacteriuria count of $> 10^5$ colony forming units/mL
- Leukocyturia of > 5 /high-power field

If a subject meets the criteria for the definition of a UTI, the investigator will record whether the UTI was "symptomatic" or "asymptomatic" on the adverse event eCRF

6.5.2 Potential Distant Spread of Toxin Adverse Events

To assess possible distant spread of toxin (PDSOT), 40 MedDRA preferred terms that may be associated with botulinum toxin effects have been identified in [Table 8](#). All AEs associated with PDSOT will be tabulated by SOC and PT; in addition, all PDSOT AEs will be listed by treatment group and subject. The 40 terms are listed below.

Table 8: MedDRA Preferred Terms for Possible Distant Spread of Toxin

Cardiac Disorders Bradycardia	Nervous System Disorders Bulbar palsy
Eye Disorders Accommodation disorder	Cranial nerve palsies multiple
Diplopia	Cranial nerve paralysis
Extraocular muscle paresis	Dysarthria
Eyelid function disorder	VIIth nerve paralysis
Eyelid ptosis	Facial paresis
Pupillary reflex impaired	Hyporeflexia
Vision blurred	Hypotonia
Gastrointestinal Disorders	Paralysis
Constipation	Paralysis flaccid
Dry mouth	Paresis cranial nerve
Dysphagia	Peripheral nerve palsy
Ileus paralytic	Peripheral paralysis
Infections and Infestations	Speech disorder
Botulism	Vocal cord paralysis
Musculoskeletal and Connective Tissue Disorders	Vocal cord paresis
Muscular weakness	Renal and Urinary Disorders Urinary retention
	Respiratory, Thoracic and Mediastinal Disorders
	Aspiration
	Diaphragmatic paralysis
	Dysphonia
	Dyspnoea
	Pneumonia aspiration
	Respiratory arrest
	Respiratory depression
	Respiratory failure
	Reproductive System and Breast Disorders
	Pelvic floor muscle weakness

6.6 Serious Adverse Events

The number and percent of subjects with serious adverse events will be tabulated by MedDRA system organ class and preferred term. In addition, a listing will be generated of subjects with serious adverse events.

6.7 Clinical Laboratory Evaluations

Urinalysis will be performed at all study visits (excluding clinic visit at Week 24) by a central laboratory; a urine culture and sensitivity test will also be performed when central laboratory

urine results are suggestive of a UTI (positive leukocyte esterase, nitrites, blood and/or microscopic sediments such as white blood cells [WBCs], red blood cells [RBCs] and/or bacteria).

For quantitative urinalysis results, actual values and changes from baseline will be summarized for each time point by treatment groups. Categorical urinalysis results will also be summarized.

Urinalysis results will be classified as low, normal, or high at each visit according to the laboratory supplied reference ranges. Shift tables of reference range changes from Baseline to each visit will be summarized.

At screening, prior to DB treatment, blood samples will be drawn from all subjects for analysis of the following laboratory tests to be performed by the central laboratory: complete blood count, creatinine, and blood urea nitrogen. All male subjects will undergo a prostate-specific antigen test also performed by the central laboratory.

All laboratory results will be listed by treatment group, subject and time point. Listings of pregnancy testing, urine dipstick testing, and urine culture sensitivity assessment will be provided separately.

